To date, reports on the clinical performance of ZAs remain controversial. Different abutment type seems to be associated with different risks, which can arise at any stage of therapy and greatly influence patient's satisfaction and quality of life. Although some clinical investigations affirmed excellent performance of ZAs with survival rate approaching 100%,^{21,22} unexpected and early catastrophic fractures of OPZAs and TPZAs with friction-fitted titanium inserts both have been reported.^{22,23} OPZAs were considered to be accompanied by higher risks of fracture, screw loosening and permanent damage due to stress concentrations, especially with internal implant connections. While TPZAs with friction-fitted titanium inserts seem to require higher machining accuracy and failure of the connection between the zirconia sleeve and titanium insert is a concern.^{21,24-26}

Even though technological progress in the field of metal-free materials has given rise to considerable improvements of these two types of abutment over the decades, there is still lack of clinical evidence for the use of two types ZAs.

Recent studies also showed that pro-inflammatory cytokines in peri-implant crevicular fluid (PICF) were significantly related to peri-implant diseases and further marginal bone loss.^{27,28} Tumor necrosis factor alpha (TNF- α) and interleukin-6 (IL-6) are pro-inflammatory cytokines that appear to have an important role in periodontal tissue destruction.^{29,30} It's necessary to quantitatively determine the concentrations of cytokines in PICF of OPZAs and TPZAs with friction-fitted titanium inserts as potential biomarkers for peri-implant disease diagnosis.

Thus, the investigators designed this randomized split-mouth clinical trial to evaluate the

clinical, radiological and immunological outcomes of OPZAs and TPZAs with friction-fitted titanium inserts in single implant crowns in aesthetic region. The primary outcome is prespecified as mechanical complication rates at 1-year follow-up.

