2. METHOD/DESIGN

Overview

The present study is designed as a prospective, single-center, split-mouth, randomized controlled clinical trial. The investigators plan to recruit several adult patients who have two missing teeth in the maxillary anterior region and plan to be restored with two single implant crowns. The clinical component of the study will be initiated in Feb. 2019 at the Department of Oral and Maxillo-facial Implantology, Shanghai Ninth People's Hospital, Shanghai Jiao Tong University, China.

All patients received oral hygiene instruction and periodontal treatment before implant surgery.

The investigators will record the age, gender, physical health of all participants and they will meet the following inclusion criteria. Peri-apical radiographs with paralleling technique will be performed on the day of final restorations delivery. Clinical radiological and immunological re-evaluations will be performed at 1 year after the final crowns delivery.

Inclusion criteria

1) age \geq 18; 2) patients with two missing teeth in esthetic region and plan to be restored with two single implant crowns; 3) adjacent to natural teeth; 4) absence of oral mucosal disease and oral infection; 5) implants with conical connection (Nobel Active, Nobel Biocare® or NobelReplace Conical Connection, Nobel Biocare®); 6) patients with the willingness to participate in the present study.

Exclusion criteria

1)Heavy smokers (>10 cigarettes/day); 2) uncontrolled periodontitis (Full mouth plaque score $>20\%$, full mouth bleeding score $>25\%$, residual pocket depth $>5\text{mm}$); 3) with systematic diseases that may affect implant therapy, such as uncontrolled diabetes mellitus (Fasting blood-glucose $>7.2\text{mmol/L}$, Glycosylated hemoglobin $>7\%$), current intake of bisphosphonates (treatment for malignancy), pregnant(or plan to get pregnant), with history of radiation therapy in head and neck region.

Recruitment

Patients who have two missing teeth in the maxillary anterior region and plan to be restored

with two single implant crowns will be recruited at the Department of Oral and Maxillo-facial Implantology, Shanghai Ninth People's Hospital, Shanghai Jiao Tong University, China. Eligible patients will receive the study information and informed consent, and any patients who do not sign the consent will not be included in the study.

Allocation and blinding

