Eligible patients have two missing teeth, and they will be randomly assigned into two groups: OPZAs group (OG): restored with the OPZAs; TPZAs group (TG): restored with the TPZAs with friction-fitted titanium bases. The study is an open-label trial without blinding.

Outcomes

All the included patients will be recalled for clinical, radiological and immunological re-evaluations 1-year after the final crowns delivery. Survival rates, mechanical complication rates, bleeding on probing (BOP%), probing depth (PD), modified plaque index (mPI), marginal bone loss (MBL), concentrations of pro-inflammatory cytokines (TNF- α , IL-6) in peri-implant crevicular fluid (PICF), and pink esthetics score/white esthetics score (PES/ WES) will be recorded.

Survival rates.²⁵ The survival rate was defined as the percentage of success implants and remained crowns which never been replaced.

Mechanical complications rates. Veneer chipping, abutments or implants fracture, screw loosening or fracture and other mechanical complications will be recorded during the 1-year

follow-up.

Peri-implant conditions. The indicators of peri-implant conditions included bleeding on probing% (BOP%), pocket probing depth (PD) and modified plaque index (mPI).

Marginal bone loss (MBL).²⁶ Peri-apical radiographs with paralleling technique will be performed on the day of final restorations delivery and 1 year later. The implant length is used as calibration reference. The distance between restoration margin and the most coronal level of implant-bone contact will be recorded. The final result calculate as the mean value of mesial and distal sites. The alteration of the distance between baseline and 1-year follow-up is defined as the MBL.

Pro-inflammatory cytokines in peri-implant crevicular fluid (PICF). The investigators will collect the patients' PICF with the paper strip (PerioPaper Strips; Oraflow Inc., Smithtown, NY, USA) at 1-year follow-up to access differences in pro-inflammatory cytokines (IL-6 and TNF- α) between two groups. Enzyme-linked immunosorbent assay (ELISA) will be used to analyzed PICF and evaluated the concentrations of cytokines. The PICF collection method and cytokines determination referred to Christopher A. Barwacz et al (Figure 2).¹⁸

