PES/WES.^{27,28} In this study, pink aesthetic score (PES) and white esthetic score (WES) will be applied for the objective esthetic assessment of the final restoration. The investigators will take patients' intraoral photos by the camera (D70, Nikon, Tokyo, Japan) at 1 year follow up. The aesthetic effect will be assessed by two specific dentists independently. They will asked to give scores for variables of PES (Mesial papilla, distal papilla, level of soft-tissue margin, soft-tissue contour, alveolar process and soft-tissue color and texture) and WES (Tooth form, tooth volume/outline, color, surface texture and transparency) with the 0-1-2 scoring system. Final

PES/WES is the sum of the two.

The primary outcome variable is presupposed to be the success rates. And the null hypothesis is that there is no significant difference regarding mechanical complication rates between two groups.

Statistical analysis

All statistical analyses will be performed using SAS software, version 9.4 (SAS Institute). Normal tests will be performed to know the normality of continuous data before appropriate ways of statistical description and analysis were chosen. Means, standard deviations (SD) and student's t test will be used for data in accordance with normal distribution. Medians, inter quartile range (IQR) and Wilcoxon Rank Sum test will be used for non-normally distributed data. Qualitative data will be described and analyzed by percentage and Chi-square Test. A two-sided *P* value of less than 0.05 will be considered to indicate statistical significance.

Missing data

Sample size calculation was performed accounting for possible loss to follow-up. Moreover, the investigators will account for the data not missing at random due to unbalanced loss to follow-up by handling drop-outs as nonsuccess using the intention-to-treat principle.

Ethical considerations

Ethical approval

All eligible patients will receive study information and informed consent, and any patients who do not sign the consent will not be included in the study.

Withdraw

All patients in this study will be informed that they have the right to withdraw at any time during the study, regardless of whether they withdraw or not, the treatment required by the patients will be accepted.

4. Discussion

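### A normality test that the plan does not specify chooses the test and summary for each continuous secondary outcome, so the effect to be estimated is not fixed in advance and no estimate or interval is named

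*Combined protocol and SAP*

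**What the plan says.** Section 2 (Method/Design), under Statistical analysis, sets a two-step rule for continuous data. First, "Normal tests will be performed to know the normality of continuous data before appropriate ways of statistical description and analysis were chosen". Then one of two branches follows:

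- If the data look normal: "Means, standard deviations (SD) and student's t test will be used for data in accordance with normal distribution".
- If they do not: "Medians, inter quartile range (IQR) and Wilcoxon Rank Sum test will be used for non-normally distributed data".

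Other outcomes take a separate route: "Qualitative data will be described and analyzed by percentage and Chi-square Test". The threshold is common to all: "A two-sided *P* value of less than 0.05 will be considered to indicate statistical significance".

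The design is a "prospective, single-center, split-mouth, randomized controlled clinical trial", described under Allocation and blinding as open-label. For the cytokines, the Outcomes subsection says "Enzyme-linked immunosorbent assay (ELISA) will be used to analyzed PICF and evaluated the concentrations of cytokines", from samples taken at 1 year. It says nothing about their distribution, scale or values below the detection limit.

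The Background makes the main endpoint binary: "The primary outcome is prespecified as mechanical complication rates at 1-year follow-up". The end of the Outcomes text names success rates instead, but that is also a rate.

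**The concern.** A rule that lets the trial's own data choose the analysis leaves two things open.

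The first is the quantity being estimated. One branch compares means and the other compares rank ordering while reporting medians. For skewed data these are different effects. IL-6 and TNF-alpha could end up on different branches and be reported in ways that cannot be set side by side.

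The second is the rule itself. The plan does not say which normality test is used, at what level, or whether it is applied to each group, the pooled values, residuals or within-patient differences. It does not say what happens if two groups give different answers. These gaps would be filled by analysts who can see allocation and outcomes.

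Neither branch yields a stated treatment effect with an interval. A reader would get two summaries and a P value for most of the clinical outcomes and all of the radiological and immunological ones. This concern is separate from the choice between paired and unpaired tests and would remain if both branches were made paired.

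**Working it through.** **Inputs.** From the documents: the two-branch rule, two-sided 0.05 and the split-mouth design. The documents give no sample size, SD, effect size, correlation or distribution, so there is no planned figure to reproduce. Assumed instead: 10 to 40 pairs; positive, right-skewed values; within-patient correlation 0 or 0.5; Shapiro-Wilk at 5% in each group, with the t test used if both groups pass and the rank test otherwise.

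**Effect size.** It was set for about 80% power of a paired t test on logs (normal approximation):

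log ratio = (1.96 + 0.84) × s × √(2(1 − ρ)) / √n

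For s = 0.8, ρ = 0.5, n = 20: 2.80 × 0.8 × 1 / 4.472 = 0.501, a ratio of exp(0.501) = 1.65.

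**Step 1: how stable is the choice of test?** Lognormal data, 4,000 trials per setting:

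| log-SD | Pairs | t test chosen |
|---|---|---|
| 0.3 | 10 | 76–79% |
| 0.3 | 20 | 56–59% |
| 0.3 | 40 | 27–30% |
| 0.5 | 10 | about 58% |
| 0.5 | 20 | about 23% |
| 0.8 or more | 15 or more | 0–11% |

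With truly normal data, 1 − 0.95² = 9.75% of trials should still go to the rank test; the simulation gave about 10%. The choice is unstable for mild to moderate skew and nearly settled for strong skew.

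**Step 2: does the choice matter?** The two branches describe different quantities. For a lognormal variable, mean/median = exp(s²/2): exp(0.08) = 1.08 at s = 0.4 and exp(0.18) = 1.20 at s = 0.6. On significance, paired t and signed-rank disagreed in 7–15% of trials (15 or 20 pairs, correlation 0.5, a real effect present). With the unpaired tests that the plan names, disagreement was 7–26% across all settings.

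**Step 3: type I error.** With paired versions of both tests, 20 pairs and correlation 0.5, the two-stage rule rejected a true null in 4.1–5.5% of trials. With the unpaired tests as written, the rate was 4.5–6.4% at zero correlation and 0.6–1.4% at correlation 0.5, where ignoring the pairing makes the test conservative.

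**Step 4: power.** Paired tests, 20 pairs, correlation 0.5; the gamma data have the same coefficients of variation and mean ratio as the lognormal:

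| | log-SD 0.4 | 0.6 | 0.8 |
|---|---|---|---|
| Lognormal, two-stage rule | 74% | 73% | 71% |
| Lognormal, always signed-rank | 73% | 72% | 71% |
| Lognormal, paired t on logs | 78% | 79% | 78% |
| Gamma, two-stage rule | 74% | 66% | 54% |
| Gamma, paired t on logs | 71% | 61% | 46% |

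- Gate against a fixed rank test: +1, +1 and 0 points, so the pre-test costs nothing visible.
- Log scale against the gate, lognormal: 78 − 74 = 4, 79 − 73 = 6, 78 − 71 = 7 points gained.
- Log scale against the gate, gamma: 74 − 71 = 3, 66 − 61 = 5, 54 − 46 = 8 points lost.

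Repeat runs of 2,000 to 3,000 trials agree to within about a point: roughly 4 to 8 gained if lognormal. A repeat for gamma put the loss at 3 to 9. At 2,500 trials the Monte Carlo standard error near 75% is √(0.75 × 0.25 / 2,500) = 0.9 points.

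**The case against.** The best defence is that a decision rule is written down, that it is common practice, and that it performs adequately. Much of this stands. The rule holds its error rate and matches a fixed signed-rank test. On lognormal data it beats always using a raw-scale paired t test: in one run 76/74/73% against 74/70/63%. For strongly skewed cytokines with 15 or more pairs, it almost always lands on the rank test.

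A reader might infer more than the documents support:

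- **That the pre-test loses power on the cytokines.** It does not. Any difference comes from the log scale, and its sign depends on a distribution that the documents do not give.
- **That the choice is close to a coin flip, with the two groups often classed differently.** Split classifications reached 45–48% at log-SD 0.4 to 0.6 with 20 patients, but about 27% at 0.8 and 13% at 1.0. All of these figures assume that each group is tested separately on raw values. The plan refers only to continuous data and does not say this.
- **That every outcome is affected.** Survival and mechanical complications are rates and go to the chi-square test.

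It can also be said that the unpaired tests are the larger defect. At correlation 0.5, moving to a paired log-scale t test gained 25 to 32 points on lognormal data. That is true, but pairing both branches would still leave the effect measure unspecified.

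What the defence does not answer is that the rule is incomplete, that the effect compared depends on the sample, and that no estimate or interval is named.

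**Conclusion.** The concern holds for the continuous secondary outcomes: PD, BOP%, mPI, MBL, IL-6, TNF-alpha and PES/WES, taking these as the ones the plan would analyse as continuous. Their analysis and effect measure depend on a normality test that is unnamed, at an unstated level, on unspecified data, in an open-label trial. The consequence is an unfixed effect measure and, in about 7 to 15% of simulated trials, a different significance verdict according to the branch taken. That figure assumes 15 or 20 pairs, lognormal values, correlation 0.5 and an effect giving about 80% power.

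It is not a finding about false positives, the primary outcome or lost power. A log scale would gain about 4 to 8 points if the cytokines are lognormal and lose about 3 to 9 if they are gamma, with 20 pairs and correlation 0.5. The documents do not allow a choice between these. The point deserves a change because the remedy is nearly free, not because the rule is seriously harmful.

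**What to change.** In the Statistical analysis section:

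1. Delete the normality test as a means of choosing the analysis.
2. Name one within-patient (paired) analysis for each continuous outcome, reporting the mean within-patient difference between abutment types with a 95% CI.
3. For IL-6 and TNF-alpha, fix the scale before any data are seen. One option is the log scale, reported as a within-patient ratio of geometric means with a 95% CI, together with a stated rule for values below the detection limit. Justify the choice by interpretability and not by a promised gain in power.
4. Report the Wilcoxon signed-rank test as a fixed sensitivity analysis for all these outcomes, whatever the distributions look like.

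The cost is a few sentences of SAP wording, with no extra patients or data. The one downside is a possible small loss of power if the chosen scale fits poorly, as the gamma results show; the signed-rank analysis would help to reveal that.

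### The trial is split-mouth, but the tests named for the binary primary outcome and for skewed outcomes are for independent samples, and the unit of randomization is unclear

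*Combined protocol and SAP*

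**What the plan says.** The title, abstract, Background and Overview all call the trial split-mouth; the Overview states "The present study is designed as a prospective, single-center, split-mouth, randomized controlled clinical trial". The inclusion criteria require two missing teeth, to be restored with two single implant crowns.

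Allocation and blinding says "Eligible patients have two missing teeth, and they will be randomly assigned into two groups", one for each abutment type. No sentence says that each patient receives one of each, or how the site for each abutment is chosen.

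The Statistical analysis section names three tests:

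- For categorical data: "Qualitative data will be described and analyzed by percentage and Chi-square Test".
- For skewed data: "Medians, inter quartile range (IQR) and Wilcoxon Rank Sum test will be used for non-normally distributed data".
- For normal data: "Means, standard deviations (SD) and student's t test will be used for data in accordance with normal distribution", without saying whether the t test is paired.

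The choice between the last two follows a check of the raw outcomes: "Normal tests will be performed to know the normality of continuous data before appropriate ways of statistical description and analysis were chosen".

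The primary outcome is stated twice. The Background has "The primary outcome is prespecified as mechanical complication rates at 1-year follow-up"; the end of the Outcomes section has "The primary outcome variable is presupposed to be the success rates".

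**The concern.** Two crowns in one mouth share the patient's bite, hygiene and biology, so their outcomes may be correlated. The rank sum test and the ordinary chi-square test compute their variance as if the two groups were unrelated. The matching procedures for a split-mouth comparison are the signed-rank test and McNemar's test. A paired t test needs normality of the within-patient differences, not of the raw values that the plan proposes to check.

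The direction of the error depends on a fact the plan leaves open. With one abutment of each type per patient, ignoring positive correlation overstates the variance and makes the test conservative. With whole patients allocated and both crowns counted as independent, it understates the variance and inflates the type I error. A reader who cannot tell which case applies cannot interpret the primary P value against its nominal 5% level.

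**Working it through.** **Inputs from the documents.** Two crowns per patient; two-sided test at 0.05; the three tests above; drop-outs counted as nonsuccess (Missing data). The documents give no sample size, event rate, power, drop-out rate or correlation, so there is no stated figure to reproduce. Everything below uses assumed values of r, event rate and number of pairs.

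**1. Large-sample size of a nominal 5% independent-samples test.**

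- One of each abutment per patient: the true variance of the difference is (1 − r) times the assumed variance, so size = 2[1 − Φ(1.96/√(1 − r))].
- Whole patients allocated, two crowns pooled: the variance is (1 + r) times the assumed variance, so size = 2[1 − Φ(1.96/√(1 + r))].

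At r = 0.2 the first is 2[1 − Φ(1.96/0.894)] = 2.8% and the second is 2[1 − Φ(1.96/1.095)] = 7.4%.

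**2. Finite-sample size.** For binary pairs, P(event on both sides) = p₁p₂ + r√(p₁q₁p₂q₂), with exact enumeration of all possible tables. The table uses 40 pairs (or 20 patients per arm under whole-patient allocation) and 10% events in both groups. The rank sum row comes from 40,000 simulated trials of 40 lognormal pairs, with r the correlation on the log scale.

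| True size, % | r = 0 | 0.1 | 0.2 | 0.3 | 0.5 |
|---|---|---|---|---|---|
| Large-sample, one of each | 5.0 | 3.9 | 2.8 | 1.9 | 0.6 |
| Chi-square, one of each | 5.9 | 4.7 | 3.6 | 2.5 | 1.0 |
| McNemar, asymptotic | 4.6 | 4.7 | 4.8 | 4.8 | 3.9 |
| Rank sum, one of each | 4.9 | 4.1 | 2.9 | 2.0 | 0.7 |
| Large-sample, whole patient | 5.0 | 6.2 | 7.4 | 8.6 | 11.0 |
| Chi-square, whole patient | 5.9 | 7.1 | 8.4 | 9.7 | 12.5 |

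At 5% events and r = 0.2, every version is conservative with 40 pairs: chi-square 2.4%, McNemar asymptotic 3.1%, mid-P 0.9%, exact 0.2%.

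**3. Correlation created by the plan's own drop-out rule.** In a split-mouth trial a lost patient is a nonsuccess on both sides. Assume 10% drop-out, 10% true events and zero natural correlation:

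- Rate on each side: 0.10 + 0.90 × 0.10 = 0.19.
- Both sides: 0.10 + 0.90 × 0.01 = 0.109.
- r = (0.109 − 0.19²)/(0.19 × 0.81) = 0.0729/0.1539 = 0.47.

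With 40 pairs, chi-square size falls to 0.9%, while asymptotic McNemar stays at 4.7%.

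**4. Power, 15% against 5%, 40 pairs.**

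| Power, % | r = 0 | 0.2 | 0.3 | 0.5 |
|---|---|---|---|---|
| Chi-square | 35 | 33 | 31 | 28 |
| McNemar asymptotic | 30 | 36 | 41 | 54 |
| McNemar mid-P | 27 | 31 | 32 | 36 |
| McNemar exact | 18 | 19 | 20 | 21 |

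At r = 0.2 the discordant proportion is 0.154, so 40 × 0.154 ≈ 6.2 discordant pairs are expected. Significance needs at least 4 (asymptotic: 4²/4 = 4 > 3.84), 5 (mid-P: 0.5⁵ = 0.031) or 6 (exact: 2 × 0.5⁶ = 0.031).

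**5. Pairs for 80% power, same rates, r = 0.2.** The usual formula, with ψ the discordant proportion and d = 0.10, is [1.96√ψ + 0.842√(ψ − d²)]²/d² = (0.769 + 0.319)²/0.01 ≈ 119. Exact enumeration gives 109 (asymptotic), 111 (mid-P) and 126 (exact).

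**The case against.** The strongest reply is that the design is stated as split-mouth throughout, and whole-patient allocation rests on one loosely worded sentence. All the material type I inflation depends on that weaker reading. Under the stated design with positive correlation, the named tests err mainly on the safe side, and a significant result would if anything be understated. That is correct. It makes the likely error conservative, but it does not make the tests suit the design. The plan's reference to unbalanced loss to follow-up also fits parallel groups better than a design in which a lost patient removes both sides.

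Second, the chi-square label could loosely include McNemar's test, and the t test could be paired. Nothing in the text says so, and naming the rank sum test rather than the signed-rank test points the other way.

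Third, the benefit of changing is uncertain. At r = 0 the chi-square test has more power than asymptotic McNemar (35% against 30%); exact McNemar has less power at every r shown; and r = 0.5 at 15% against 5% is close to the attainable maximum of about 0.55. This stands: the case is validity, not a promised gain in power. Asymptotic McNemar is not strictly bounded at 5% either. It stayed at or below 4.84% in 21 enumerated null scenarios with 20 to 40 pairs, but reaches about 5.3% at 80 to 120 pairs with 15% events, a trivial excess.

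**Conclusion.** The concern holds. The analysis named for the binary primary outcome and for skewed outcomes does not match the stated design, and the plan does not establish the unit of randomization that decides the direction of the error. For r between 0.1 and 0.5, the large-sample size of the nominal 5% test runs from 3.9% down to 0.6% with one of each abutment per patient, and from 6.2% up to 11.0% with whole-patient allocation. The true size cannot be fixed from the documents, and with no correlation and no drop-out the error is negligible. Zero correlation is hard to rely on, however, because the drop-out rule itself creates concordant pairs. For the t test the criticism is narrower: its form is unspecified and normality is checked on the wrong quantity. Treating both versions of the primary outcome as binary per crown is an inference, since success is not defined. This must be fixed, because choosing between paired and unpaired tests, or between McNemar versions, after seeing the data could change the conclusion.

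**What to change.** 1. In Allocation and blinding, state what is randomized. If the design is split-mouth as titled, say that the two sites within each patient are randomized, one to each abutment, and how.
2. In Statistical analysis, for mechanical complications and survival or success, name McNemar's test with its version (asymptotic, mid-P or exact) fixed in advance, and report the paired risk difference with a 95% confidence interval.
3. For continuous outcomes, name the paired t test or the signed-rank test, check normality on the within-patient differences, and report the within-patient difference with a 95% confidence interval.
4. If whole patients are in fact randomized, use a patient-level or cluster-adjusted analysis instead.
5. Name one primary outcome, and restate the sample size on discordant pairs.

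The cost is wording in two sections and different SAS options, with no new data or procedures. The sample-size restatement is the larger task: the plan mentions a calculation but gives no number, event rate or power, so whether the planned enrolment suffices cannot be judged. The choice of McNemar version also has a price. The exact test is safe but can lose power when discordant pairs are few (19% against 33% for the unpaired chi-square at 40 pairs, 15% against 5%, r = 0.2).

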2. OBJECTIVES AND HYPOTHESIS

The purpose of the present study is to evaluate the clinical, radiological and immunological outcomes of the OPZAs and TPZAs with friction-fitted titanium bases in single implant crowns in aesthetic region. Survival rates, mechanical complication rates, bleeding on probing (BOP%), probing depth (PD), modified plaque index (mPI), marginal bone loss (MBL), concentrations of pro-inflammatory cytokines (TNF- α , IL-6) in peri-implant crevicular fluid (PICF), and pink esthetics score/white esthetics score (PES/ WES) will be included in the comparison indicators. The null hypothesis is that there is no significant difference regarding mechanical complication rates between two groups.

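### The binary primary outcome rests on an unpaired chi-square P value, with no effect estimate, no confidence interval and no method for small counts

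*Combined protocol and SAP*

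**What the plan says.** The Statistical analysis section (under 2. METHOD/DESIGN) gives one rule for all categorical outcomes: "Qualitative data will be described and analyzed by percentage and Chi-square Test". The decision criterion follows: "A two-sided *P* value of less than 0.05 will be considered to indicate statistical significance". The section does not say whether the chi-square is continuity-corrected, and it names no exact test, paired test, effect measure or interval.

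The rule governs the primary outcome under either of the plan's definitions. The Background says "The primary outcome is prespecified as mechanical complication rates at 1-year follow-up"; the Outcomes section says "The primary outcome variable is presupposed to be the success rates". Both are binary.

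The hypothesis section states: "The null hypothesis is that there is no significant difference regarding mechanical complication rates between two groups". The Outcomes section repeats this. No equivalence or non-inferiority margin is given.

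On size, the Overview says only that "The investigators plan to recruit several adult patients who have two missing teeth in the maxillary anterior region". The Missing data section says "Sample size calculation was performed accounting for possible loss to follow-up", but no input or result is shown. No complication rate appears anywhere. The nearest figure is a Background remark that some studies found survival close to 100%.

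**The concern.** Each patient contributes one site to each arm, so the two results are paired. An ordinary chi-square treats them as independent samples. It is also a large-sample test, and a single-centre trial of one-year mechanical complications may yield only a handful of events. A few events on one side could then be called significant or not according to which chi-square the programmer runs. With no events at all, the plan would produce no primary test result.

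More often P would be above 0.05. Percentages and a P value would not tell the reader which differences in complication rate remain plausible. The trial aims to inform the choice between two abutment types, so that is the information its users need.

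**Working it through.** **Inputs.** From the documents: binary primary outcome, two sites per patient, two-sided 0.05, chi-square. Assumed, because the documents are silent: number of patients n (30 for illustration, with other values where shown) and complication rates of 2% to 20%. There is no figure in the plan to reproduce.

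**1. When are counts sparse?** Expected events per arm = n × rate, so an expected count of 5 needs n = 5 / rate.

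| Rate | Patients needed |
|---|---|
| 2% | 250 |
| 5% | 100 |
| 10% | 50 |
| 15% | 34 |
| 20% | 25 |

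**2. One table, several P values.** Take 4 of 30 vs 0 of 30.
- Uncorrected chi-square: 60 × (4×30 − 0×26)² / (30×30×4×56) = 864,000 / 201,600 = 4.286, P = 0.038.
- Continuity-corrected: 60 × (120 − 30)² / 201,600 = 2.411, P = 0.121.
- Fisher: 2 × C(30,4) / C(60,4) = 2 × 27,405 / 487,635 = 0.112.
- Exact McNemar (4 discordant pairs, all one way): 2 × 0.5⁴ = 0.125.

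At 5 vs 0 the same four tests give 0.020, 0.062, 0.052 and 0.0625. For 4 vs 0 the uncorrected chi-square is below 0.05, and Fisher and exact McNemar above it, at each n checked from 15 to 60. Exact McNemar needs at least 6 discordant pairs, all one way (2 × 0.5⁶ = 0.031).

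**3. No events.** At 0 vs 0 the chi-square denominator is zero and there is no test. With independent sites and a 2% rate in both arms, the chance of this with 30 patients is 0.98⁶⁰ = 30%; at 5% it is 0.95⁶⁰ = 5%.

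**4. Average type I error.** Enumerating all tables for the uncorrected chi-square with 30 per arm and independent sites gives 0.3% at a 2% rate, 2.8% at 5% and 5.4% at 10%. The largest value found for n = 15 to 60 and rates of 2% to 20% was 5.9% (n = 40, 10%). With within-patient correlation 0.3 it was 0.3% to 2.5% (n = 20 to 40, rates 5% to 10%), so ignoring the pairing makes the test conservative.

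**5. How often is P at or above 0.05?** Assume true rates of 10% vs 2%, independent sites, full enumeration.

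| Test | 30 pairs | 50 pairs |
|---|---|---|
| Uncorrected chi-square (one reading of the plan) | 78% | 62% |
| Exact McNemar (an alternative) | 96% | 80% |

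At 5% vs 15% the power of the uncorrected chi-square is 15% with 20 patients, 26% with 30, 35% with 40 and 46% with 60.

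**6. What an interval would show.** The 95% paired score (Tango) interval at 30 pairs:
- 0 vs 0: limits ± z² / (n + z²) = 3.84 / 33.84, that is −11.4 to +11.4 points.
- 3 vs 0: −2.5 to +25.6 points.
- 4 vs 0: +0.5 to +29.7 points, although exact McNemar gives P = 0.125.

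**The case against.** **Sparse data are not documented.** This stands. Survival is a different outcome from mechanical complications, which also include chipping and screw loosening, and the Background reports early fractures too. At 20% with 25 or more patients the expected counts are adequate. Counting drop-outs as failures could raise the counts further, although a patient who is lost takes both sites and adds only a concordant pair. Sparsity must therefore stay conditional.

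**The chi-square does not inflate error.** A reader might infer from the 4 vs 0 example that the plan yields too many false positives. Step 4 does not support that. Part of the disagreement is the conservatism of exact McNemar itself, whose type I error is about 1.0% at 30 pairs and a 10% rate. With continuity correction the chi-square agrees with the exact tests at 4 vs 0 and 5 vs 0. What remains is that the plan does not say which version applies.

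**The plan does not say that P ≥ 0.05 means equal performance.** A null worded as no significant difference tempts a reader to infer that a non-significant result would be taken as confirming it. The documents define only what counts as significant; they do not say how a non-significant result will be reported. The wording is loose, and correcting it is mainly clerical.

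**An exact test lowers power.** True, and the cost is stated with the fix. It is a reason to choose the McNemar version deliberately and to put the interval first. It is not a reason to keep an unpaired test.

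**Conclusion.** The concern holds in a limited form. On the text alone, the primary comparison has no effect estimate, no interval, no small-count method and no allowance for pairing, and the version of the chi-square is unstated. The point about pairing takes the design as split-mouth, as the title and Overview describe it.

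The practical size depends on assumptions. With 30 pairs and few events, the choice of chi-square version moves P from 0.038 to 0.121 on the same data, and a table without events gives no result. At 10% vs 2% the uncorrected chi-square misses significance in about 78% of trials with 30 pairs and 62% with 50. The 96% and 80% figures belong to exact McNemar and should not be read as describing the planned test. The problem fades with larger samples or rates near 20%, but the plan does not show which case applies.

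The documents do not support a charge of inflated type I error or of a planned claim of equivalence. This is a worthwhile and cheap improvement to the analysis; it does not invalidate the design.

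**What to change.** In the Statistical analysis section, for the primary outcome:

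1. Make the main result the paired difference in proportions with its 95% score confidence interval.
2. Replace the chi-square with a McNemar test and name its version, exact or mid-P, in advance.
3. State that this P value decides significance and the interval describes precision, because the two can disagree (4 vs 0 in step 6).
4. State that P ≥ 0.05 will be reported as no difference shown, together with the interval, and not as equal performance.

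A minor change: in the hypothesis and Outcomes sections, reword the null as equal mechanical complication rates for the two abutments.

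**Cost.** A few sentences and a few lines of code; no extra patients, visits or measurements. The real price is fewer significant results. At 30 pairs and 10% vs 2%, power is about 22% with the uncorrected chi-square, 11% with mid-P McNemar and 4% with exact McNemar. The intervals will also show openly how imprecise the trial is.
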